9.1.3 Study Procedures and Assessments

In the event of recurrent COVID-19 restrictions on in-person study visits, processes are in place to provide home delivery of study drug using an external courier service, and study visits may be conducted by phone or video conference. The study will permit continued study drug dosing and study participation with up to 2 missed laboratory and ECG assessments when those are scheduled less than or equal to 8 weeks apart, and up to 1 missed laboratory or ECG assessment when they are rescheduled greater than 8 weeks apart.

9.1.3.1 Medication Washout and Screening Period (Week -6 through Week -1)

Subjects are to undergo a screening visit 1 to 6 weeks prior to the planned first day of study treatment. Screening may occur over multiple visits within the 6-week screening period if clinically indicated (for example, to allow for washout of prohibited medications). However, subjects should be randomized as soon as it is determined they meet all study inclusion/exclusion criteria.

Any required medication washout should be completed prior to initiating collection of the WI-NRS in the e-Diary.

Subjects whose washout equals or exceeds the 6-week screening window should complete laboratory and ECG screening as early as possible. This ensures that the washout period is not prolonged unnecessarily, and they can resume non-study treatment for their itch in the event that they fail laboratory or ECG criteria. Those who complete the washout and are otherwise eligible for study participation will be permitted to re-screen with written consent from the Medical Monitor.

Subjects who fail their initial screening due to the requirement for an extended medication washout may be re-screened at the discretion of the Medical Monitor and with written permission from the Sponsor. In cases of other unique circumstances that may justify re-screening, Investigators must contact the Medical Monitor to discuss the specific conditions under which subjects may qualify for re-screening.

Screening assessments are as follows:

- Obtain written informed consent (must be completed first, before any screening assessments are performed)
- Review eligibility criteria
- Record medical, neurological, and PN history
- Physical examination
- Brief neurological assessment
- Vital signs
- Record height, weight, and body mass index (BMI)
- Central ECG (triplicate)

- Clinical laboratory assessments
- Urinalysis
- Quantitative serum pregnancy tests will ONLY be conducted at the initial screening visit, and again at baseline, to confirm non-pregnant status prior to dispensation of investigational product. Once on study, subjects will be expected to adhere to protocol required birth control requirements and serum pregnancy testing will not be done at regularly scheduled intervals.
- Urine pregnancy test (woman of childbearing potential [WOCBP])
- Record and assess AEs, concomitant medications, and therapies (including restricted and prohibited medications)
- Dispense electronic diary (e-diary) at least 7 days prior to projected baseline visit, train on its use
- Review ability to comply with e-diary entry use in the Trialogics portal and counsel and/or retrain subject as needed.
- Dispense and train on use of the Subject Symptom Log and Subject Medication Log
- ItchyQoL
- PAS
- Investigator Global Assessment-Prurigo Nodularis (IGA-PN)
- PBI-P
- Sleep Scale (PROMIS Sleep Disturbance Short Form 8a)

9.1.3.2 Double-blind Titration Period (Weeks 1 and 2)

The subject will return for the Week 1 baseline visit, at which point it will be determined if the subject meets the entry criteria. If the subject meets all inclusion/exclusion criteria, the subject will be randomized and the titration period will begin. During the double-blind titration period, subjects will have 1 study site visit (baseline visit), just prior to entering Week 1 and 2 telephone contacts, followed by 1 end of titration visit at Week 2.

Baseline Visit (Week 1, Day 1)

The following procedures will be performed during this visit:

- Confirm eligibility against inclusion/exclusion criteria ([Section 9.5](#)) and perform e-diary eligibility assessment
- Brief neurological assessment
- Vital signs and weight
- Clinical laboratory assessments
- Quantitative serum pregnancy tests will ONLY be conducted at the initial screening visit, and again at baseline, to confirm non-pregnant status prior to dispensation of investigational

product. Once on study, subjects will be expected to adhere to protocol required birth control requirements and serum pregnancy testing will not be done at regularly scheduled intervals.

- Urinalysis
- Urine pregnancy test (WOCBP)
- Randomization via Interactive Web Response System (IWRS)
- Blood sample for PK analysis
- Record and assess AEs, concomitant medications, and therapies
- Review Subject Symptom Log and Subject Medication Log and re-dispense (or issue new logs as needed)
- Review e-diary entry and retrain on use or compliance as needed
- WI-NRS (should be entered by subject via e-diary [prior to randomization] if not entered prior to the visit; reminder that subject should enter WI-NRS score via e-diary daily through the Week 14 visit)
- ItchyQoL
- PAS
- IGA-PN
- PBI-P (“Importance of Treatment Goal” questions only)
- Sleep Scale (PROMIS Sleep Disturbance Short Form 8a)
- Photography (if applicable)
- Dispense investigational product (Blister card)
- Dispense Instructions for Taking TR11 Study Medication (Double-blind titration blister card)

Telephone Contacts 1 and 2 (Week 1, Day 3 and Week 1, Day 7)

During the telephone contact, the following will be assessed and documented:

- Tolerability intervention (See [Section 10.6.3](#))
- Record and assess AEs, concomitant medications, and therapies
- WI-NRS (reminder that subject should enter WI-NRS score via e-diary or Trialogics web portal daily through the Week 14 visit)

End of Titration Visit (Week 2, Day 14)

The following procedures will be performed during this visit:

- Brief neurological assessment
- Vital signs

- Central ECG (triplicate)
- Clinical laboratory assessments
- Tolerability intervention (See [Section 10.6.3](#))
- Urine pregnancy test (WOCBP)
- Blood sample for PK analysis
- Record and assess AEs, concomitant medications, and therapies
- Review Subject Symptom Log and Subject Medication Log and re-dispense (or issue new logs as needed)
- Retrieve e-diary data and review compliance
- Dispense investigational product (bottle)
- Dispense Instructions for Taking TR11 Study Medication (Double-blind fixed dose bottle)
- Investigational product accountability
- Review investigational product compliance
- WI-NRS (reminder that subject should enter WI-NRS score via e-diary or Trialogics web portal daily through the Week 14 visit)

9.1.3.3 Double-blind Fixed-dose Period (Weeks 3 to 14)

During the 12-week double-blind fixed-dose period, there will be 2 telephone contacts (TelephoneContacts 3 and 4) and 3 study visits.

Telephone Contacts 3 and 4 (Week 3, Day 15 and Week 3, Day 21)

During the telephone contacts, the following will be assessed and documented:

- Tolerability intervention (Week 3, Days 15 and 21 only; Day 15 is first day of 162 mg BID for active treatment group, see [Section 10.6.3](#))
- Record and assess AEs, concomitant medications, and therapies
- WI-NRS (reminder that subject should enter WI-NRS score via e-diary or Trialogics web portal daily through the Week 14 visit)

Week 6 Visit

The following procedures will be performed during this visit:

- Vital signs
- Central ECG (triplicate)
- Clinical laboratory assessments
- Urine pregnancy test (WOCBP)

- Blood sample for PK analysis
- Record and assess AEs, concomitant medications, and therapies
- Review Subject Symptom Log and Subject Medication Log and re-dispense (or issue new logs asneeded)
- Retrieve e-diary data and review entry compliance
- ItchyQoL
- Sleep Scale (PROMIS Sleep Disturbance Short Form 8a)
- WI-NRS (reminder that subject should enter WI-NRS score via e-diary or Trialogics web portaldaily through the Week 14 visit)
- Dispense investigational product (bottle)
- Retrieve investigational product and containers
- Investigational product accountability
- Review investigational product compliance

Week 10 Visit

The following procedures will be performed during this visit:

- Vital signs
- Urine pregnancy test (WOCBP)
- Blood sample for PK analysis
- Record and assess AEs, concomitant medications, and therapies
- Review Subject Symptom Log and Subject Medication Log and re-dispense (or issue new logs asneeded)
- Retrieve e-diary data and review entry compliance
- ItchyQoL
- PAS
- IGA-PN
- PBI-P (“Treatment Benefit Assessment” questions only)
- Sleep Scale (PROMIS Sleep Disturbance Short Form 8a)
- WI-NRS (reminder that subject should enter WI-NRS score via e-diary or Trialogics web portaldaily through the Week 14 visit)
- Dispense investigational product (bottle)
- Retrieve investigational product and containers
- Investigational product accountability

- Review investigational product compliance

Week 14 Visit

The following procedures will be performed during this visit:

- Physical Examination
- Vital signs
- Central ECG (triplicate)
- Clinical laboratory assessments
- Urine pregnancy test (WOCBP)
- Blood sample for PK analysis
- Record and assess AEs, concomitant medications, and therapies
- Review Subject Symptom Log and Subject Medication Log and re-dispense (or issue new logs as needed)
- Retrieve e-diary data and review entry compliance
- ItchyQoL
- PAS
- IGA-PN
- PBI-P (“Treatment Benefit Assessment” questions only)
- Sleep Scale (PROMIS Sleep Disturbance Short Form 8a)
- WI-NRS (last daily entry) to be entered by subject via e-diary or Trialogics web portal; reminder that all future entries will occur during visits via the Trialogics web portal or the e-diary.
- Photography (if applicable)
- Dispense investigational product (blister card)
- Dispense Instructions for Taking TR11 Study Medication (open-label titration blister card)
- Retrieve investigational product and containers
- Investigational product accountability
- Review investigational product compliance

9.1.3.4 Extension Titration Period (Weeks 15 and 16)

During the 2-week extension titration period, there will be 2 telephone contacts (Telephone Contacts 5 and 6) and 1 end of titration study visit at Week 16.

Telephone Contacts 5 and 6 (Week 15, Day 101 and Week 15, Day 105)

During the telephone contacts, the following will be assessed and documented:

- Tolerability intervention (See [Section 10.6.3](#))
- Record and assess AEs, concomitant medications, and therapies

End of Titration Visit (Week 16, Day 112)

The following procedures will be performed during this visit:

- Brief neurological assessment
- Vital signs
- Central ECG (triplicate)
- Urine pregnancy test (WOCBP)
- Blood sample for PK analysis
- Record and assess AEs, concomitant medications, and therapies
- WI-NRS to be entered by the subject via Trialogics web portal or e-diary
- Review Subject Symptom Log and Subject Medication Log and re-dispense (or issue new logs as needed)
- Retrieve e-diary data and review entry compliance
- Dispense investigational product (bottle)
- Dispense Instructions for Taking TR11 Study Medication (open-label fixed dose bottle)
- Investigational product accountability
- Review investigational product compliance

9.1.3.5 Open-label Fixed-dose Period (Weeks 17 to 52)

During the 36-week open-label fixed-dose period, there will be 2 telephone contacts (TelephoneContacts 7 and 8) and study visits will occur in the clinic every 4 or 8 weeks.

Telephone Contacts 7 and 8 (Week 17, Day 113 and Week 17, Day 120)

During the telephone contacts, the following will be assessed and documented:

- Tolerability intervention (See [Section 10.6.3](#))
- Record and assess AEs, concomitant medications, and therapies

Week 20 Visit

The following procedures will be performed during this visit:

- Vital signs
- Central ECG (triplicate)
- Blood sample for PK analysis
- Urine pregnancy test (WOCBP)
- Record and assess AEs, concomitant medications, and therapies
- Review Subject Symptom Log and Subject Medication Log and re-dispense (or issue new logs as needed)
- Retrieve e-diary data and review entry compliance
- ItchyQoL
- PAS
- IGA-PN
- PBI-P (“Treatment Benefit Assessment” questions only)
- Sleep Scale (PROMIS Sleep Disturbance Short Form 8a)
- WI-NRS to be entered by subject via Trialogics web portal or e-diary
- Dispense investigational product (bottle)
- Investigational product accountability
- Review investigational product compliance

Week 24 Visit

The following procedures will be performed during this visit:

- Vital signs
- Urine pregnancy test (WOCBP)
- Record and assess AEs, concomitant medications, and therapies
- Review Subject Symptom Log and Subject Medication Log and re-dispense (or issue new logs as needed)
- Retrieve e-diary data and review entry compliance
- ItchyQoL
- PAS
- IGA-PN
- Sleep Scale (PROMIS Sleep Disturbance Short Form 8a)
- WI-NRS to be entered by subject via Trialogics web portal or e-diary
- Dispense investigational product (bottle)

- Retrieve investigational product and containers
- Investigational product accountability
- Review investigational product compliance

Week 28 Visit

The following procedures will be performed during this visit:

- Vital signs
- Central ECG (triplicate)
- Clinical laboratory assessments
- Blood sample for PK analysis
- Urinalysis
- Urine pregnancy test (WOCBP)
- Record and assess AEs, concomitant medications, and therapies
- Review Subject Symptom Log and Subject Medication Log and re-dispense (or issue new logs asneeded)
- Tolerability intervention (See [Section 10.6.3](#))
- Retrieve e-diary data and review entry compliance
- ItchyQoL
- PAS
- IGA-PN
- PBI-P (“Treatment Benefit” questions only)
- Sleep Scale (PROMIS Sleep Disturbance Short Form 8a)
- WI-NRS to be entered by subject via Trialogics web portal or e-diary
- Photography (if applicable)
- Assess whether subject is eligible for down titration based on criteria of confirmed WI-NRS ≤ 3 and 1 category improvement in PAS lesion healing (PAS item 5b). For example, if “0-24%” of PN lesions at baseline were assessed as ‘healed’, then a 1-category change means that “25-50%” of current Week 28 PN lesions are now healed. If both criteria are met, the option for a permanent dose reduction to 108 mg BID may be discussed. Note: if criteria are met, this decision is at the discretion of the Investigator and with the agreement of the subject, but once dose reduction has been initiated no re-escalation is permitted
- Dispense investigational product (bottle)
- Retrieve investigational product and containers
- Investigational product accountability

- Review investigational product compliance

Week 32 Visit

The following procedures will be performed during this visit:

- Vital signs
- Blood sample for PK analysis
- Urine pregnancy test (WOCBP)
- Record and assess AEs, concomitant medications, and therapies
- Review Subject Symptom Log and Subject Medication Log and re-dispense (or issue new logs as needed)
- Retrieve e-diary data and review entry compliance
- PAS
- IGA-PN
- WI-NRS to be entered by subject via Trialogics web portal or e-diary
- Assess whether subject is eligible for down titration based on criteria of confirmed WI-NRS ≤ 3 and 1 category improvement in PAS lesion healing (PAS item 5b). For example, if “0-24%” of PN lesions at baseline were assessed as ‘healed’, then a 1-category change means that “25-50%” of current Week 28 PN lesions are now healed. If both criteria are met, the option for a permanent dose reduction to 108 mg BID may be discussed. Note: if criteria are met, this decision is at the discretion of the Investigator and with the agreement of the subject, but once dose reduction has been initiated no re-escalation is permitted
- Dispense investigational product (bottle)
- Retrieve investigational product and containers
- Investigational product accountability
- Review investigational product compliance

Week 36 Visit

The following procedures will be performed during this visit:

- Vital signs
- Blood sample for PK analysis
- Urine pregnancy test (WOCBP)
- Record and assess AEs, concomitant medications, and therapies
- Review Subject Symptom Log and Subject Medication Log and re-dispense (or issue new logs as needed)

- Tolerability intervention (See [Section 10.6.3](#))
- Retrieve e-diary data and review entry compliance
- ItchyQoL
- PAS
- IGA-PN
- PBI-P (“Treatment Benefit Assessment” questions only)
- Sleep Scale (PROMIS Sleep Disturbance Short Form 8a)
- WI-NRS to be entered by subject via Trialogics web portal or e-diary
- Assess whether subject is eligible for down titration based on criteria of confirmed WINRS ≤ 3 and 1 category improvement in PAS lesion healing (PAS item 5b). For example, if “0-24%” of PN lesions at baseline were assessed as ‘healed’, then a 1-category change means that “25-50%” of current Week 28 PN lesions are now healed. If both criteria are met, the option for a permanent dose reduction to 108 mg BID may be discussed. Note: if criteria are met, this decision is at the discretion of the Investigator and with the agreement of the subject, but once dose reduction has been initiated no re-escalation is permitted
- Dispense investigational product (bottle)
- Retrieve investigational product and containers
- Investigational product accountability
- Review investigational product compliance

Week 44 Visit

The following procedures will be performed during this visit:

- Vital signs
- Clinical laboratory assessments
- Blood sample for PK analysis
- Urine pregnancy test (WOCBP)
- Record and assess AEs, concomitant medications, and therapies
- Review Subject Symptom Log and Subject Medication Log and re-dispense (or issue new logs as needed)
- Retrieve e-diary data and review entry compliance
- ItchyQoL
- PAS
- IGA-PN
- PBI-P (“Treatment Benefit Assessment” questions only)

- Sleep Scale (PROMIS Sleep Disturbance Short Form 8a)
- WI-NRS to be entered by subject via Trialogics web portal or e-diary
- Dispense investigational product (bottle)
- Retrieve investigational product and containers
- Investigational product accountability
- Review investigational product compliance

9.1.3.6 Washout and Safety Follow-up Period and Last Contact

The washout and safety follow-up period begins after the subject discontinues investigational product; regardless of when this occurs. The Off-Treatment visit procedures will occur at the Week 52 (end of treatment) visit for subjects who complete the study or upon premature, permanent discontinuation of investigational product at any time during the study, regardless of reason (other than withdrawal of consent).

The last clinic visit will occur at the end of the washout period; 14 days post discontinuation of dosing. The Last Visit should be scheduled 2 weeks after the Off-Treatment visit and the End of Study telephone call will occur 4 weeks after investigational product discontinuation.

If a subject discontinues the study early, the specific instructions in [Section 9.6](#) Premature Discontinuation of Investigational Product Treatment take precedence.

Off-Treatment Visit (Week 52, Day 364 or at Premature Discontinuation)

The following procedures will be performed during this visit:

- Physical examination
- Brief neurological assessment
- Vital signs
- Central ECG (triplicate)
- Clinical laboratory assessments
- Blood sample for PK analysis
- Urinalysis
- Urine pregnancy test (WOCBP)
- Record and assess AEs, concomitant medications, and therapies
- Review Subject Symptom Log and Subject Medication Log and re-dispense (or issue new logs as needed)
- Retrieve e-diary data
- ItchyQoL

- PAS
- IGA-PN
- PBI-P (“Treatment Benefit Assessment” questions only)
- Sleep Scale (PROMIS Sleep Disturbance Short Form 8a)
- WI-NRS to be entered by subject via Trialogics web portal or e-diary
- Photography (if applicable)
- Launch Subjective Opiate Withdrawal Scale (SOWS) via the subject status update to “Off-treatment/Week 52 (Activate SOWS)” in the Trialogics portal. The SOWS will be activated and subjects should be instructed to complete the questionnaire daily for the next 14 days.
For subjects who discontinue study drug early (including in-between study visits), the change in subject status to “Off-treatment/Week 52 (Activate SOWS)” in the Trialogics portal should be made immediately as the site becomes aware of discontinuation;
SOWS entries provide valid information ONLY if they are collected in the first 14 days off-treatment.
- Retrieve investigational product and containers
- Investigational product accountability
- Review investigational product compliance

Last Study Visit (Week 54, Day 378)

The following procedures will be performed during this visit:

- Physical examination
- Brief neurological assessment
- Vital signs
- Clinical laboratory assessments
- Urine pregnancy test (WOCBP)
- Record and assess AEs, concomitant medications, and therapies
- WI-NRS to be entered by subject via Trialogics web portal. Review Subject Symptom Log and Subject Medication Log and collect for filing in source records
- Retrieve e-diary
- Retrieve the 14-day SOWS, review data and assess need for withdrawal intervention

End of Study Telephone Call (Telephone Contact 9; Week 56, Day 392)

During this telephone contact, the following will be assessed and documented:

- Record and assess AEs, concomitant medications, and therapies

- Ask the subject to verbally report their current WI-NRS score and site staff must enter the reported score into the Trialogics web portal. The recommended question text is: “On a scale of zero to ten, with zero being ‘no itch’ and 10 being the ‘worst imaginable itch’, how would you describe your worst itch experience over the last 24 hours?”

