6. **AEs** are to be continually assessed starting with the signing of the informed consent. Subjects should continue to record any new AEs or concomitant medication use on the Subject Symptom Log and Subject Medication Log. Site staff are required to remind subjects to bring the logs to each visit (including the telephone contacts). Logs should be reviewed by site staff at every visit prior to re-dispensing (or issuing new logs as needed) to subjects. Final retrieval of the logs, for filing in source records, should occur at the last clinic visit. **Events of special interest should trigger the collection of additional information using the AESI worksheet and documented under the AESI section of the Adverse Event eCRF.** Event details and both subject and investigator narratives should be thoroughly documented in the AESI worksheet and completed under the AESI section of the Adverse Event eCRF. Referto [section 12.1.1. Definitions](#).
7. **PROs** (Patient Reported Outcomes) are to be administered by site staff or e-diary as described in the Trialogics User Manual. WI-NRS data will also be collected from the subject via the Trialogics web portal at each clinic visit (beginning at Week 20).
8. **Photography:** To be performed at certain sites only. See the Canfield Quick Reference Guide and User Reference Manual for photography procedures as applicable.
9. The 14-day **SOWS** is to be completed, on the e-diary, at home by the subject. Site staff must change the subject's status to "Off-treatment" on the Trialogics web portal to

Table-2.**Schedule of Assessments – Open-label Extension Period**

Study Period →	Assessment ↓	Open-label Fixed-dose Period								Washout and Safety Follow-up Period		Last Contact for WI-NRS
		Repeating visit q4wk or q8wk								Off-Treatment ¹	Last Visit ¹	End of Study telephone call ¹
		W17 to W52										
Visit Week		17	17	20	24	28 ²	32 ²	36 ²	44	52	54	56
Study Day (±2 days)		113	120	140	168	196	224	252	308	364	378	392

trigger the launch of the SOWS. Subjects must be instructed to enter SOWS data daily for the 14 days following discontinuation of investigational product regardless of when this occurs (i.e. Week 52 visit or Premature Discontinuation). Data should be reviewed by site staff during the 14-day collection period in order to assess the need for any withdrawal intervention. The e-diary is to be retrieved at the last clinic study visit.

10. (B) Applicable if subject discontinues before Week 52.

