9.6 Premature Discontinuation of Investigational Product Treatment

Subjects who complete investigational product treatment through the full study treatment course are considered to have completed treatment with the investigational product (even if some doses have been missed). Subjects who discontinue investigational product, prior to 52 weeks of treatment will be considered to have prematurely discontinued and will be asked to complete the following visits (unless consent is withdrawn):

- If the decision to discontinue treatment is made during an onsite study visit (scheduled or unscheduled), perform the procedures and assessments outlined in the Off-Treatment visit, regardless of where they are in the study visit schedule.
- If the decision to discontinue treatment is made while the subject is not at a study visit, schedulea visit as soon as logically possible, but no later than 2 weeks later, to perform the procedures and assessments described in the Off-Treatment visit. Upon notification that the subject has permanently stopped dosing, the site should immediately update the subject’s status on the Trialogics web portal, in order to launch the SOWS, and instruct the subject to begin entering their SOWS data daily via the e-diary for the next 14 days.
- Schedule the subject to return to the clinic 2 weeks after completion of the Off-Treatment visit and perform the procedures and assessments outlined in the Last Visit, regardless of where they are in the study visit schedule.

- Schedule the End of Study telephone call with the subject 4 weeks after completion of the Off- Treatment visit and perform the procedures and assessments outlined in the schedule of events for this visit, regardless of where they are in the study visit schedule.
- If discontinuation of investigational product occurs any time between Day 1 and the Week 14 visit, the subject will be asked to complete the Off-Treatment visit, the Last Visit, and the End of Study visit telephone call, and to return to the clinic for the study schedule planned Week 14 visit.

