7.4. Handling of missing data and outliers

7.4.1. Missing data analysis methods

For the primary efficacy endpoint, missing values at week 14 will be set to missing. The data will be analysed using the mixed model technique. The analysis assumes that the missing data is missing at random (MAR). Thus, it provides an unbiased estimate of the treatment effect that would have been observed had all subjects continued on treatment until Week 14. It therefore assumes that the response for withdrawn subjects will follow the trajectory of the respective treatment after discontinuation. In order to assess the robustness of the results to the MAR assumption, a sensitivity analysis will be conducted under

the assumption that the data is missing not at random (MNAR). The details of this analysis are described in

For the change from baseline in ItchyQoL and PROMIS, all observed data up to and including Week 14 will be used without using imputation methods for missing data. However, in sensitivity analyses, two multiple imputation (MI) methods will be used: Control based multiple Imputation and Tipping Point Analysis approaches

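### For subjects who stop drug before about Day 64 to 78, the site takes back the e-diary before the Day 92–98 window of the primary endpoint, and nothing directs them to the web portal instead

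*Protocol*

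**What the plan says.** **Device collection.** The Last Study Visit list in Protocol 9.1.3.6 has "Retrieve e-diary". The lists for other visits, including Off-Treatment, retrieve e-diary data, so the Last Visit entry reads as the device itself. Table-2 footnote 9 says: "The e-diary is to be retrieved at the last clinic study visit".

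**Early stoppers.** Section 9.1.3.6 gives Section 9.6 precedence when a subject discontinues early. Section 9.6 tells the site: "Schedule the subject to return to the clinic 2 weeks after completion of the Off-Treatment visit", and to "perform the procedures and assessments outlined in the Last Visit, regardless of where they are in the study visit schedule". If the decision to stop is made away from a visit, the Off-Treatment visit follows as soon as possible, "but no later than 2 weeks later, to perform the procedures". Subjects who stop before Week 14 are also asked "to return to the clinic for the study schedule planned Week 14 visit".

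**Daily scoring.** Table-1 footnote 7 has WI-NRS recorded daily, by e-diary or Trialogics web portal, until the Week 14 visit. Protocol 11.2.1 lets the portal serve as a backup when the diary is inaccessible for whatever reason. The Week 14 visit itself takes one entry by either route.

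**Scoring rule.** SAP 7.3.1 averages Days 92–98. With fewer than five values it averages those that exist, after topping up from later days and then from the three days before Day 92. It states no minimum. Baseline needs at least five values (SAP 7.2.1).

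**Missing Week 14 score.** Protocol 13.4.6.1 counts it as non-response. SAP 7.4.1 says "missing values at week 14 will be set to missing", and SAP 8.6 (Analysis of Primary Efficacy Endpoint) repeats this.

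**The concern.** The Week 14 return visit exists so that subjects who stop drug still contribute Week 14 data. The primary endpoint, however, comes from a week of daily home scores that ends on Day 98, and the written procedure can remove the main recording tool weeks earlier. After an early Last Visit, the only WI-NRS value that the plan secures is the single entry at the Week 14 visit.

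Two things are at stake. A single score is a noisier basis for a four-point responder rule than an average of five to seven, and it would be compared with a baseline that had to contain at least five. If no value exists, the two documents treat the subject differently: non-responder in the protocol, left missing under a missing-at-random assumption in the SAP. Under the SAP, data lost through a logistics rule enter the primary estimate as an assumption about what would have been observed.

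**Working it through.** The plan gives no figure for when early stoppers lose the device, so the check is calendar arithmetic.

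**Inputs**
- S = study day on which drug is stopped.
- g = delay from stopping to the Off-Treatment visit, 0 to 14 days (Protocol 9.6).
- Off-Treatment to Last Visit = 14 days (Protocol 9.6). Table-2 agrees: 378 − 364 = 14.
- Endpoint window = Days 92–98, with Days 89–91 as top-up (SAP 7.3.1).
- Visit window ±2 days (Table-2).
- Assumption: the device is usable through the day before the Last Visit.

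**Formulas**
- Last Visit day: L = S + g + 14. Last device day: L − 1 = S + g + 13.
- No device day in Days 92–98: S + g + 13 < 92, so S ≤ 78 − g.
- No device day in Days 89–98 either: S + g + 13 < 89, so S ≤ 75 − g.
- At least five device days in Days 92–98: S + g + 13 ≥ 96, so S ≥ 83 − g.
- All seven: S + g + 13 ≥ 98, so S ≥ 85 − g.

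| Delay g | None of Days 92–98 if S ≤ | None of Days 89–98 if S ≤ | At least 5 of 7 if S ≥ | All 7 if S ≥ |
|---|---|---|---|---|
| 0 | 78 | 75 | 83 | 85 |
| 7 | 71 | 68 | 76 | 78 |
| 14 | 64 | 61 | 69 | 71 |

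The ±2-day window moves the first cut-off to between 64 − 2 = 62 and 78 + 2 = 80.

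**What this means for the score**
- A subject who stops by Day 75 − g and does not use the portal has only the Week 14 visit entry. Under SAP 7.3.1 that one value becomes the Week 14 score.
- A subject who stops on Day 76 − g to 78 − g can add one to three diary values from Days 89–91.
- A subject who does not come back and does not use the portal has no score.

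**Size.** The only drop-out data are from TR03, in Protocol 13.1: 12 of 18 completed on NAL ER 162 mg and 20 of 22 on placebo. Non-completion was therefore 6/18 = 33% and 2/22 = 9%. Stop days are not given. Protocol 7.2.3 says adverse events tended to come in the first weeks of dosing, and Protocol 9.3 that early gastrointestinal and nervous-system effects can limit treatment. Many stops may therefore fall before the cut-off.

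**The case against.** The strongest reply is that losing the device is not losing the data. Table-1 footnote 7 names the portal as a route for daily entry up to Week 14, and the reminders at the visits and telephone contacts after baseline repeat it. The backup provision in Protocol 11.2.1 is wide enough to cover a returned diary. This stands as far as permission goes. However, Section 9.6 does not ask early stoppers to attend the intermediate contacts where the reminders are given, and no text sends them to the portal after the Last Visit.

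Second, the SAP scores even one value, so a returning subject has a thin score rather than a missing one. This is correct. Missing scores arise only when the subject neither returns nor uses the portal.

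Third, the Week 14 visit keeps its value because it also collects ItchyQoL, PAS and PROMIS, the key secondary instruments. This is also correct. A reader might infer that the device rule defeats the purpose of the return visit, and the documents do not support that.

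Fourth, footnote 9 could mean the Week 14 visit for a subject who returns then. That reading is possible but not secure, because Section 9.1.3.6 uses the same idea of a last clinic visit for the end of the two-week washout. Likewise, Table-1 uses the word retrieve at routine visits where scoring goes on, and the Last Visit list is headed Week 54. Sites could read these texts differently.

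Finally, WI-NRS collection follows the Trialogics User Manual, which is not part of the documents and may cover portal entry after device return.

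**Conclusion.** The point holds as a gap in the written procedure for subjects who stop drug before about Day 64 to 78. The device is collected before the endpoint window, the same subjects are asked back for Week 14, and no instruction secures the daily scores in between. Their Week 14 average may rest on one value or be missing. The cut-off assumes nominal visit days and a device usable until the day before the Last Visit.

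Three stronger readings are tempting and not supported:
- That early stoppers cannot record Days 92–98. The portal is a written daily route.
- That all early stoppers are affected. Those who stop from about Day 71 to 85 onwards, depending on g, hold the device for the whole window, and those in between hold it for part.
- That TR03 predicts about 60 against 16 affected subjects (33% and 9% of 180 per arm). That projects every TR03 non-completer from arms of 18 and 22. The affected group is only those who stop before the cut-off, stay in the study and do not use the portal, and Protocol 13.1 expects fewer drop-outs than in TR03.

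The number affected is unknown. TR03 suggests only that it may be larger on active drug. The correction is nearly free and protects primary data, so it should be made.

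**What to change.** For subjects who stop drug before Week 14:
- collect the e-diary at the later of the Last Visit and the Week 14 visit;
- state that daily WI-NRS, by diary or portal, continues through Day 98 unless consent is withdrawn.

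Bring Protocol 9.1.3.6, Section 9.6 and Table-2 footnote 9 into line with Table-1 footnote 7. In the same pass, reconcile the SAP's General study design text, which requires early stoppers to attend all remaining visits up to Week 14, with Protocol 9.6 and with the SAP's own Table 1 footnote 10, which ask only for the off-treatment contacts and Week 14.

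The cost is a short change to the protocol and site instructions, devices kept some weeks longer, and some added diary burden for subjects who are off drug.
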